
AASIS = Alopecia Areata Symptom Impact Scale; HBV= hepatitis B virus; HCV = hepatitis C virus
 
 All subsequent visits and week increments should be based on the date of Visit 2. All visit windows are <math>\pm 3</math> days.
 
 Serum pregnancy test only for females of childbearing potential.
 
 Includes hematology and serum chemistry.
 
 Will include thyroid stimulating hormone and hemoglobin A1c at Screening only.
 
 Includes total cholesterol, low-density lipoprotein, high-density lipoprotein, and triglycerides.
 
 Collected at Day 1 and Week 4 (pre-dose, and post-dose at end of visit), and Weeks 2 (pre-dose with clinical labs), and Weeks 8, 24 (post-dose at end of visit).
	
 Collected at Day 1 and Week 2 (pre-dose with clinical labs), and Weeks 4, 8, 24 (post-dose at end of visit). Collected pre-dose.
 
 Should be performed by the same rater for the patient for the duration of the study.
 
 Collection is ongoing.
 
 Also serves as the Early Termination Visit for patient withdrawal.
 
 Randomization/Day 1 may occur any time after Screening laboratory results are available and reviewed by the Investigator.
 
 The Safety Follow-Up Visit is intended for those patients in Cohort 1 and Cohort 2, and those patients in Cohort 3 who do not roll over into the Open-label Extension.

---	--

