### **8.1. Patient Inclusion Criteria**

1. Written informed consent, and authorization for release and use of protected health information.
2. Between 18 and 65 years of age, inclusive, at the time of informed consent.
3. Definitive diagnosis of alopecia areata with a current episode of at least 6 months and not exceeding 10 years at the time of Screening. Total disease duration greater than 10 years is permitted.
4. At least 50% scalp hair loss, as defined by a SALT score  $\geq 50$ , at Screening and Baseline.
5. If of reproductive age, willing and able to use a medically highly effective form of birth control during the study and for 30 days following last dose of study medication.  
Examples of medically highly effective forms of birth control are:
  - a. Surgical sterility (via vasectomy, hysterectomy or bilateral ligation) or post-menopausal females
  - b. Sexual partner is sterile, or of the same sex
  - c. Implants of levonorgestrel in females
  - d. Oral contraceptive (combined or progesterone only) in females
  - e. Double-barrier method (any combination of physical and chemical methods)
  - f. Intrauterine device in females, or other method with published data showing that the lowest expected failure rate is less than 1% per year
6. Willing to comply with the study visits and requirements of the study protocol.

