13. Screening labs outside the normal range for parameters associated with potential risk for treatment under investigation. This will include but is not limited to:
  - a. Platelets  $\leq 120 \times 10^9/L$
  - b. Absolute neutrophil count  $\leq 1.5 \times 10^9/L$
  - c. Hemoglobin levels  $\leq 11$  g/dL for females, or hemoglobin levels  $\leq 12.5$  g/dL for males
14. Screening blood glucose levels of hemoglobin A1c  $\geq 6.5\%$  (48 mmol/mol).
15. Abnormal liver function at Screening, defined as  $\geq 1.5 \times$  ULN of serum alanine transaminase, serum aspartate transaminase, serum alkaline phosphatase, or total bilirubin (unless isolated Gilbert's syndrome).
16. Abnormal renal function (estimated glomerular filtration rate  $<60$  mL/min/1.73 m^2 using the MDRD equation) at Screening.
17. Any active infection at Screening, active or previous Hepatitis B or C infection, or known human immunodeficiency virus infection.
18. Vaccination with herpes zoster vaccine or any live virus vaccine within 6 weeks before Screening or during the study.
19. Positive purified protein derivative test for non-bacillus Calmette-Guérin-vaccinated patients, positive QuantiFERON®-TB Gold test, or history of incompletely treated or untreated tuberculosis.
20. History of prolonged QT syndrome or a Screening QTc interval with Fridericia's correction (QTcF)  $> 450$  msec for males or QTcF  $> 470$  msec for females.
21. History of alcohol, medication, or illicit drug abuse within 1 year before the first dose of study drug.

22. Females who are nursing, pregnant, or planning to become pregnant while in the study, and for 30 days after last dose of study medication.
23. Participation in another investigational study within the greater of 4 weeks or 5 half-lives of an investigational medication prior to screening or during the study.
24. Use of strong CYP3A4 inhibitors (such as, but not limited to clarithromycin, conivaptan, grapefruit juice, indinavir, itraconazole, ketoconazole, lopinavir/ritonavir, mibefradil, nefazodone, nelfinavir, posaconazole, saquinavir, telaprevir, telithromycin, voriconazole, or fluconazole) dosed for systemic exposure.
25. Use of strong CYP3A4 inducers (such as, but not limited to barbiturates, carbamazepine, efavirenz, glucocorticoids, modafinil, nevirapine, oxcarbazepine, phenobarbital, phenytoin, pioglitazone, rifabutin, rifampin, St. John's Wort, or troglitazone) dosed for systemic exposure.

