#### **9.4.3. Study Drug Preparation and Administration**

No study drug preparation is required. Patients will take the first dose of study drug in the clinic on Day 1 and will be instructed to take study drug every 12 hours for the duration of the Treatment Period. Patients should dose study drug in the clinic on all Study Visit Days after clinical laboratory blood draws are completed.

Study drug should be taken at approximately the same times each day, with water, and with or without meals. Patients should be instructed to take study drug as prescribed according to the Week, Day, and Time of day designations in the dosing card. If a dose is missed, the patient should skip the missed dose and resume dosing at the next scheduled dose. The patient should not take two doses at the same time. Deviations from prescribed dosing should be discussed at each visit for assessment of compliance and retraining when necessary.

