#### **11.1.4. Pregnancy**

The Sponsor must be informed within 24 hours upon learning that a patient, or male patient's partner, has become pregnant any time after the first dose of study drug until 30 days after the last dose of study drug. The Pregnancy Notification eCRF should be used to report the pregnancy to the Sponsor or its designee. Patient pregnancies (or pregnancy of a male patient's partner) must be followed until termination of pregnancy or the birth of the child. The Pregnancy Outcome eCRF should be used to report information regarding the status of the infant.

If a female partner of a male patient taking investigational product becomes pregnant, the male patient taking the investigational product should notify the Investigator, and the pregnant female partner should be advised to call her healthcare provider immediately.

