#### **11.1.6. Reporting Adverse Events**

The Investigator must report to Sponsor or its designee all adverse events that occur during the study from the time written informed consent is given until the final study visit or early termination, regardless of their relationship to the study drug. Serious adverse events and pregnancies will be reported from the time written informed consent is given through 30 days beyond the last dose of study drug.

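### Women who complete 24 weeks of dosing and do not enter the extension have no scheduled pregnancy test after the last dosing day, although the protocol sets a 30-day post-dose pregnancy window

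*Protocol*

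**What the plan says.** Four provisions of the protocol carry a 30-day post-dose window that concerns pregnancy:

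- Contraception (Section 8.1, criterion 5): "birth control during the study and for 30 days following last dose of study medication".
- Eligibility (Section 8.2, criterion 22), which excludes "Females who are nursing, pregnant, or planning to become pregnant while in the study, and for 30 days after last dose of study medication".
- Notification (Section 11.1.4): the sponsor is told if a patient or a male patient's partner "has become pregnant any time after the first dose of study drug until 30 days after the last dose of study drug".
- Reporting (Section 11.1.6): "Serious adverse events and pregnancies will be reported from the time written informed consent is given through 30 days beyond the last dose".

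In Table 1 the pregnancy-test row is marked at Screening, Day 1 and Weeks 4, 8, 12, 16, 20 and 24. It is blank at Week 28. SAP Section 17.2 shows the same pattern, so a misread table is unlikely. Footnote 2 defines the test: "Serum pregnancy test only for females of childbearing potential".

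The laboratory entry at Week 28 does not supply the test. Footnote 3 describes that entry as "Includes hematology and serum chemistry", and Table 5 lists serum hCG in a column of its own.

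Dosing continues to the Week 24 visit. Section 9.4.3 says "Patients should dose study drug in the clinic on all Study Visit Days after clinical laboratory blood draws are completed", and Section 10.7 takes a post-dose pharmacokinetic sample at Week 24. Footnote 13 reserves Visit 11 for Cohorts 1 and 2 and for "those patients in Cohort 3 who do not roll over into the Open-label Extension".

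**The concern.** A pregnancy conceived in the last days of dosing is exposed to the drug but may be too recent to show in that day's test. Earlier in treatment the next 4-weekly test would pick it up. After Week 24 there is no next test, even though the patient returns 4 weeks later and gives blood.

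From then on, detection is passive. It depends on the patient reporting the pregnancy, on the examination and adverse event review at Visit 11, or on testing that the Investigator chooses to order (Sections 10.11 and 10.13). The duty to notify in Section 11.1.4, and the follow-up to birth or termination, begin only once someone knows. The by-patient pregnancy listing in SAP Section 9.2 has the same limit.

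What is at stake is the completeness of safety information on exposed pregnancies.

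**Working it through.** The plan gives no figure of its own here to reproduce. The check is a reading of the schedule followed by day counts.

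**Inputs**

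- Test visits: Table 1 and SAP Section 17.2.
- Visit timing: footnote 1 of Table 1. All visits are counted from Visit 2, each with a window of ±3 days. Week 24 is day 168 and Week 28 is day 196.
- Post-dose window: 30 days (Sections 8.1, 8.2, 11.1.4 and 11.1.6).
- Time from conception to a positive serum hCG, L: not in the documents. Assumed to be 7 to 14 days.

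**Step 1: count the tests.** Screening, Day 1 and Weeks 4, 8, 12, 16, 20 and 24 make 8 tests, 7 of them from Day 1 on. There are 0 at Week 28.

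**Step 2: see which dosing intervals have a later test.** Dosing spans 24 / 4 = 6 four-week intervals. Those ending at Weeks 4, 8, 12, 16 and 20 (5 of 6) are each followed by another test 4 weeks after they end. The interval from Week 20 to Week 24 is not.

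**Step 3: what Week 24 can miss.** A conception less than L days before the Week 24 test is not yet detectable. With L = 7 to 14, that is the last 7 to 14 days of dosing. Whether the sample is drawn before or after that day's dose makes no difference.

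**Step 4: where a Visit 11 test would fall.** (196 ± 3) − (168 ± 3) = 28 ± 6, or 22 to 34 days after Week 24.

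**Step 5: exposed conceptions.** A conception on or before the last dose is at least 22 days old at Visit 11. Since 22 > 14, all are detectable. This holds for any lag shorter than 22 days, so it is not sensitive to the assumption.

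**Step 6: post-dose conceptions.** The latest detectable day after the last dose is the visit interval minus L:

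| Visit 11, days after Week 24 | L = 14 | L = 7 |
|---|---|---|
| Earliest, 22 | 8 | 15 |
| Nominal, 28 | 14 | 21 |
| Latest, 34 | 20 | 27 |

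The nominal reach is day 14 to 21, with extremes of day 8 and day 27. No case reaches day 30.

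**The case against.** The strongest reply is that nothing in the protocol is broken. The four 30-day provisions are a contraception duty, an eligibility rule, a notification duty and a reporting period, and none calls for a test. A reader might infer that the blank cell contradicts the 30-day window. The documents do not support that, because a period for reporting is not a promise to test throughout it. This part of the reply stands in full.

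A second reply is that capture is partly handled elsewhere. Section 11.1.4 ties notification to when the pregnancy began, so on that wording an exposed conception recognised after Week 28 is still notifiable. Unscheduled visits are also available. This stands as a mitigation, but it works only when someone notices.

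A reader might also infer that no patient is tested after the last dose. That is too broad. Under Section 8.3.1 and footnote 11 of Table 1, patients who stop early have the Week 24 assessments, including the pregnancy test, at the Early Termination Visit. Section 8.3.1 foresees that dosing may already have stopped by then. A patient discontinued for an interruption of more than 21 days (Section 9.2.1) could be tested more than 21 days after the last dose. The point is therefore confined to patients who complete dosing. Cohort 3 patients who roll over are also outside it, because they have no Visit 11.

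Finally, the yield should be small. Contraception is mandatory over the same 30 days. Late post-dose conceptions probably carry little exposure: Section 4.4.1 puts the half-life of ruxolitinib at about 3 hours, although the visible text gives none for CTP-543. This stands, and it limits the importance of the point. It does not answer the case of a conception while dosing continues.

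**Conclusion.** The gap is real and minor. It concerns women of childbearing potential who complete 24 weeks of dosing and do not enter the extension: all such women in Cohorts 1 and 2, and those in Cohort 3 who do not roll over. Their last scheduled test is on the last dosing day. With an assumed hCG lag of 7 to 14 days, a conception in the last 7 to 14 days of dosing can go undetected by any scheduled test.

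It would be tempting to say that a Week 28 test closes the 30-day window. It does not. Even the most favourable combination in the working stops at day 27. What the test does secure is detection of conceptions that occurred while the patient was still taking drug.

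The documents do not allow an estimate of how many women or pregnancies are involved, and the number should be low. Efficacy, power and alpha are unaffected.

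**What to change.** In protocol Table 1 and SAP Section 17.2, mark the existing serum pregnancy test for females of childbearing potential at Week 28 (Visit 11), using the blood already drawn there.

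The cost is one hCG assay per such woman. The visit, the blood draw and the assay all exist already. No other section needs to change.

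Timing limits the benefit. SAP Section 11 shows that Cohorts 1 and 2 already had Week 24 data when the SAP was written, so an amendment made at that stage would act mainly on Cohort 3 patients who do not roll over. The same cell is worth marking in any later protocol that reuses this schedule.

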### 3. LIST OF ABBREVIATIONS AND DEFINITIONS OF TERMS

**Table 2: Abbreviations and Specialist Terms**

Abbreviation or Specialist Term	Explanation
AASIS	Alopecia Areata Symptom Impact Scale
BID	Twice daily dosing
CFR	Code of Federal Regulations
CGI-I	Clinical Global Impression of Improvement
CTCAE	Common terminology criteria for adverse events
CYP3A4	Cytochrome P450 3A4
DMC	Data monitoring committee
DMP	Data Management Plan
eCRF	Electronic case report form
FDA	Food and Drug Administration
GCP	Good Clinical Practice
HIV	Human Immunodeficiency Virus
ICF	Informed consent form
ICH	International Conference on Harmonisation
IRB	Institutional Review Board
JAK	Janus kinase
LLN	Lower Limit of Normal
MDRD	Modification of Diet in Renal Disease
MedDRA	Medical Dictionary for Regulatory Activities
NDA	New Drug Application
PCS	Potentially clinically significant
PGI-I	Patient Global Impression of Improvement
QTc	QT interval corrected for heart rate
QTcF	QT interval corrected for heart rate (Fridericia's method)
SALT	Severity of Alopecia Tool
STAT	Signal transducers and activators of transcription
TEAE	Treatment-emergent adverse events
ULN	Upper Limit of Normal
VAS-S	Visual Analog Scale of Severity

## 4. INTRODUCTION

### 4.1. Overview of Alopecia Areata

Alopecia areata is an autoimmune disorder characterized by patches of non-scarring alopecia affecting scalp and body hair. Alopecia areata is clinically heterogeneous, affects men and women, and has a prevalence rate of 0.1% to 0.2% of the United States population [Safavi, 1992]. There is no preventative therapy or cure. Alopecia areata often presents as a cyclical disorder marked by unpredictable periods of hair loss and spontaneous regrowth, and variation in the degree or pattern of hair loss gives rise to different subtypes of alopecia areata, such as patchy, ophiasis, totalis, or universalis. Approximately 7% of patients have severe disease with almost complete hair loss and little or no regrowth [Villasante Fricke, 2015]. Onset can occur at any age and affects both men and women over the course of their lifetime. Approximately 80% of alopecia areata patients experience the first episode of hair loss by 40 years of age and 40% by 20 years of age [Villasante Fricke, 2015]. Alopecia areata can have a psychological impact with high rates of depression [Sellami, 2014] and anxiety reported, particularly in children and adolescents [Bilgic, 2013], and therefore, psychological counseling is often recommended as part of the standard of care [Al-Mutairi, 2011].

A cause for alopecia areata has not yet been identified, though as in other autoimmune disorders, genetic susceptibility and a wide array of environmental triggers are thought to be involved. Presently, treatments for alopecia areata include moderately effective intralesional corticosteroid injections or topicals, or aesthetic disguises such as makeup and wigs. Other treatments include off-label use of topical clobetasol propionate (Clobex®), approved for psoriasis (NDA 021535), or pimecrolimus (Elidel® cream 1%), approved for atopic dermatitis (NDA 021302); however, each has significant adverse reactions associated with its use, such as Cushing's syndrome, hyperglycemia, and diabetes mellitus for Clobex, and a black box warning of rare malignancies for Elidel. Currently, no existing therapies for alopecia areata have been approved by the United States Food and Drug Administration (FDA), indicating a significant unmet medical need.

### 4.2. Scientific Rationale for the Study

Concert has applied its deuterium chemical entity platform to ruxolitinib (Jakafi®), a selective Janus Kinase (JAK) inhibitor that modulates immune response through reduced intracellular JAK1 and JAK2 signaling. CTP-543 is structurally similar to ruxolitinib with the exception of eight deuterium atoms substituted in place of hydrogen. CTP-543 is being developed as a potential oral treatment for alopecia areata.

The mechanism of hair loss in alopecia areata appears to be mediated by cytotoxic T cell attack of the hair follicle after loss of immune privilege, regulated by upstream JAK signaling [Xing, 2014]. Therefore, directed JAK inhibition may represent a viable therapeutic approach to treating alopecia areata.

The JAKs are intracellular tyrosine kinases that play a central role in the signaling of cytokine and growth factor receptors [Ghoreschi, 2009]. Cytokine-induced receptor conformation changes activate the JAKs and trigger phosphorylation of the 6-member signal transducers and activators of transcription (STAT) protein transcription factor family. Upon phosphorylation, STATs dimerize and translocate to the nucleus to regulate gene transcription. Therapies that inhibit cytokine signaling or downstream JAK signaling have demonstrated efficacy in autoimmune disorders such as psoriasis, psoriatic arthritis, and rheumatoid arthritis, and multiple

JAK inhibitors are in development for autoimmune disorders such as atopic dermatitis, systemic lupus erythematosus and others.

Ruxolitinib (Jakafi®) is a selective JAK inhibitor that was launched in the United States by Incyte Corporation in 2011 as the first therapeutic agent to decrease splenomegaly and ameliorate symptoms in primary or secondary myelofibrosis, and was most recently approved in the United States in 2014 for the treatment of polycythemia vera. Ruxolitinib is currently under development by Incyte Corporation for additional hematological malignancies as well as essential thrombocythemia, graft-versus-host disease, and as a topical formulation for atopic dermatitis and vitiligo.

A pilot study (NCT01950780) conducted by Columbia University demonstrated clinical evidence for efficacy of oral ruxolitinib dosed at 20 mg BID (the approved dose for myelofibrosis) in patients with moderate to severe alopecia areata [Xing, 2014]. The majority of these patients (9 out of 12) exhibited extensive hair regrowth within 3 to 6 months of treatment initiation, averaging a 92% reduction in hair loss from baseline [Mackay-Wiggan, 2016]. In this population, ruxolitinib was considered well tolerated. In addition, there are three other case studies and one academic clinical trial (NCT02197455 and NCT02312882) that have successfully treated patients with alopecia areata using JAK inhibitors [Craiglow and King, 2014; Jabbari et al, 2015; Harris, 2016; Crispin, 2016].

### 4.3. Preclinical Information for CTP-543

[REDACTED] The CTP-543 Investigator's Brochure should be consulted for more detailed technical information, current discussion of nonclinical evaluations, and relevant information regarding the known safety profile of CTP-543 to date, and potential safety concerns based on known effects of ruxolitinib.

### 4.4. Clinical Information

#### 4.4.1. Pharmacokinetics and Clinical Safety of Ruxolitinib

The oral dose pharmacokinetics, pharmacodynamics, and safety and tolerability of ruxolitinib were evaluated in 2 double-blind, randomized, placebo-controlled studies in healthy volunteers. The first study evaluated single ascending doses from 5 mg up to 200 mg, and the second study evaluated multiple ascending doses, including both once daily and twice daily administration for 10 days, up to a total daily dose of 100 mg. In both studies, ruxolitinib was generally safe and well tolerated, with 100 mg once daily and 25 mg twice daily established as the maximum tolerated doses, respectively. The dose-limiting toxicity in the multiple ascending dose study was Grade 4 neutropenia [Shi, 2011].

Ruxolitinib demonstrated dose-linear pharmacokinetic parameters, steady-state achievement within 24 hours consistent with a short half-life of approximately 3 hours, and insignificant accumulation upon repeat dosing.

The pharmacodynamics of ruxolitinib, evaluated by the inhibition of phosphorylated STAT3, showed good correlation with ruxolitinib plasma concentrations.

Ruxolitinib was subsequently evaluated in 2 double-blind, randomized, placebo-controlled clinical trials in patients with myelofibrosis and 1 open-label, active-controlled clinical trial in

patients with polycythemia vera. The warnings and precautions section of the prescribing information for Jakafi, most recently updated in December 2017, includes thrombocytopenia, anemia and neutropenia; risk of infection; non-melanoma skin cancer; lipid elevations; and symptom exacerbation following interruption or discontinuation [Jakafi, 2017].

Recommendations for management of cytopenias include dose reduction or interruption, and monitoring of complete blood counts every 2 to 4 weeks until stabilized, and as clinically indicated thereafter. Serious infections reported include tuberculosis, progressive multifocal leukoencephalopathy, herpes zoster, and hepatitis B; all signs and symptoms of infection should be managed promptly. Periodic skin examinations are recommended to detect non-melanoma skin cancers including basal cell, squamous cell and Merkel cell carcinoma. Lipid elevations including total cholesterol, low-density lipoprotein, high-density lipoprotein, and triglycerides should be assessed every 8 to 12 weeks for monitoring and treatment of hyperlipidemia.

